8.1.2 Secondary study parameters/endpoints

- the SUV tumor-to-background ratio
- the SUV tumor-to-‘healthy salivary gland tissue’ ratio.
- The correlation between the SUV and the degree of immunohistochemical PSMA expression of the primary tumor on archival tissue.
- The establishment of new metastatic lesions.

8.1.3 Other study parameters

- Birth date
- Gender
- General medical history
- Medication use
- Allergies
- ACC/SDC history: diagnosis date, location primary tumor, TNM stage at diagnosis, ex-PA?, AR-status, HER2-status, type of surgery, date of surgery, postoperative radiotherapy, date of radiotherapy, adjuvant systemic therapy, location of recurrence, date of recurrence, palliative treatments
- Laboratory tests: MDRD, AST, ALT
- Pathology: immunohistochemical PSMA expression on archival tissue

8.2 Randomisation, blinding and treatment allocation

Not applicable

8.3 Study procedures

- Interview to collect background data

- During the screening visit the participants will be asked questions to obtain background data, such as birth data, past medical history, current medication use and allergies.
- Review of electronic patient file
 - Participants will be asked their consent for review of their patient file in order to obtain specific background data, such as type of surgery performed and date of surgery.
- Laboratory tests
 - If not performed within the last 14 days, AST, ALT and creatinine levels will be tested. All test will be done by the Clinical Chemical Laboratory of the Radboudumc. For this, blood will be taken with a 3 ml lithium-heparin tube (light-green cap). The remaining blood will be destroyed after the laboratory tests were performed.
- ⁶⁸Ga-PSMA-PET/CT imaging
 - The patients will be injected with ⁶⁸Ga-PSMA with a dose of 2MBq/kg body weight and PET/CT scanning (from groin to skull top, 3 minutes per bed position, 4-5 bed positions) will be performed 45-60 minutes post injection.
- Pathology: PSMA staining
 - On archival tissue, PSMA expression will be evaluated immunohistochemically in order to correlate immunohistochemical PSMA expression to the SUV.

8.4 Withdrawal of individual subjects

Subjects can leave the study at any time for any reason if they wish to do so without any consequences. The investigator can decide to withdraw a subject from the study for urgent medical reasons.

8.5 Replacement of individual subjects after withdrawal

If a subject decides to withdraw, another patient will be recruited until 15 ACC and 10 SDC patients have completed the study protocol.

8.6 Follow-up of subjects withdrawn from treatment

Subjects who decide to withdraw, will not get study related follow-up.

8.7 Premature termination of the study

As ^{68}Ga -PSMA-PET/CT imaging is a imaging modality often used in prostate cancer, we do not expect unforeseen side effect of this imaging modality. If unexpected side effect do appear in this patient group, termination of the study will be considered, depending on the seriousness and frequency.

9. SAFETY REPORTING

9.1 Temporary halt for reasons of subject safety

In accordance to section 10, subsection 4, of the WMO, the sponsor will suspend the study if there is sufficient ground that continuation of the study will jeopardise subject health or safety. The sponsor will notify the accredited METC without undue delay of a temporary halt including the reason for such an action. The study will be suspended pending a further positive decision by the accredited METC. The investigator will take care that all subjects are kept informed.

9.2 AEs, SAEs and SUSARs

9.2.1 Adverse events (AEs)

Adverse events are defined as any undesirable experience occurring to a subject during the study, whether or not considered related to the trial procedure. All adverse events reported spontaneously by the subject or observed by the investigator or his staff will be recorded.

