3. STUDY DESIGN

Design: diagnostic study which evaluates the level of PSMA expression in ACC/SDC patients with ^{68}Ga -PSMA-PET/CT imaging in order to establish whether these patients are eligible for ^{177}Lu -PSMA therapy.c

Duration: each patients has to make 2 additional visits (apart from normal patient care) when he or she participates in this study. These 2 visits will take approximately 3 hours in total.

Setting: single center study (Radboud university medical center, Nijmegen, the Netherlands)

[figure not shown]

Figure 4. Flow chart of study procedures.

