6.5 Description and justification of route of administration and dosage

The final formulation of the product is ^{68}Ga - PSMA-HBED-CC in ethanol 7% in PBS (14 ml), 2MBq / kg / body weight ^{68}Ga , 10 μg PSMA-HBED-CC, which is administered intravenously in a single injection. This is in line with previous studies on the investigational product for prostate cancers patients.

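### Adverse events are captured passively after the injection, so the side-effect frequency that section 8.7 weighs may be underestimated and has no defined denominator

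*Combined protocol and SAP*

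**What the plan says.** Section 9.2.1 defines an adverse event broadly, as "any undesirable experience occurring to a subject during the study, whether or not considered related to the trial procedure". It then states how such events enter the record: "All adverse events reported spontaneously by the subject or observed by the investigator or his staff will be recorded".

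Section 8.7 says what side effects could lead to. It begins "If unexpected side effect do appear in this patient group" and continues that "termination of the study will be considered, depending on the seriousness and frequency". It gives no threshold, denominator or observation window.

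The exposure is the product described in section 6.5, "which is administered intravenously in a single injection". Under section 8.3 the scan "will be performed 45-60 minutes post injection". Section 3 says of the study visits: "These 2 visits will take approximately 3 hours in total". The only questioning listed in 8.3 is the background interview at the screening visit. No symptom enquiry, checklist, telephone call or visit is listed after the injection.

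On numbers, section 8.5 says that after a withdrawal "another patient will be recruited until 15 ACC and 10 SDC patients have completed the study protocol". Section 8.6 adds that subjects who withdraw have no study-related follow-up.

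**The concern.** Section 8.7 asks the investigators to judge a frequency. A frequency needs a numerator collected in the same way from everyone and a stated denominator, and the plan supplies neither. Under the rule in 9.2.1, a subject who had a symptom, did not mention it and showed no sign of it is recorded exactly like a subject who had none. An error of this kind can only lower the count.

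At stake is how much weight a low or zero count can bear. Section 13.1 says that the product has not been evaluated before in these two tumour types, and section 13.2 bases its safety expectation on patients with prostate cancer. The subjects in this study are a chance to check that expectation. Section 9.3 also requires a yearly safety report with a full safety analysis. Section 9.5 dispenses with a DSMB, so the judgement in 8.7 rests on what the investigators record.

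**Working it through.** The plan states no side-effect rate, capture rate or stopping threshold, and section 4.4 says that an exact sample size calculation does not apply. There is therefore no figure of the plan's own to reproduce. The check is a reading of the sections, followed by an illustration on assumed values.

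**Reading**

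1. Capture routes in 9.2.1: spontaneous report and observation by the investigator or staff. Asking is not listed, and it is not forbidden.
2. Planned questioning in 8.3: at screening only, before the injection.
3. Time on site after the injection: 45 to 60 minutes of waiting, then 4 to 5 bed positions at 3 minutes each, which is 12 to 15 minutes. In total that is 45 + 12 = 57 to 60 + 15 = 75 minutes. Staff can see visible reactions in this period. They cannot see symptoms that are felt but not voiced, or anything after departure.
4. Denominator: 15 + 10 = 25 subjects complete the study. Those who withdraw are replaced, so the number injected can exceed 25, and 8.7 does not say which number applies.

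**Illustration**

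Inputs: n = 25 (sections 4.4 and 8.5). The true share of subjects with a side effect, p, is assumed to be 10% or 20%. The share of those that is recorded, c, is assumed to be 1, 2/3 or 1/3. Subjects are taken as independent, with the same c for each event.

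Probability that no event is recorded = (1 − p × c)^25

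| p | c = 1 | c = 2/3 | c = 1/3 |
|---|---|---|---|
| 10% | 0.9000^25 = 0.072 | 0.9333^25 = 0.178 | 0.9667^25 = 0.428 |
| 20% | 0.8000^25 = 0.004 | 0.8667^25 = 0.028 | 0.9333^25 = 0.178 |

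The same effect appears in the upper limit for a zero count. With 0 of 25 recorded, the exact one-sided 95% upper limit for the recorded rate is 1 − 0.05^(1/25) = 0.113. Dividing by c gives the limit for the true rate: 0.113 at c = 1, 0.113 ÷ 2/3 = 0.169 at two thirds, and 0.113 ÷ 1/3 = 0.339 at one third.

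The c = 1 column is a ceiling and does not predict what asking would achieve. A question put before departure misses later events. If it brought capture to 80%, for example, the chance of recording none at a 10% true rate would be (1 − 0.08)^25 = 0.124, not 0.072.

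**The case against.** The strongest reply is that section 9.2.1 states its rule openly, nothing elsewhere contradicts it, and the safety system does not depend on 8.7. Section 9.1 obliges the sponsor to suspend the study if continuing would jeopardise subjects. Sections 9.2.2 and 9.2.3 set reporting duties for serious events and unexpected serious reactions. Mild symptoms that nobody mentions are also the least likely to change a judgement that weighs seriousness as well as frequency. Safety is neither an objective nor an endpoint, section 10 plans no adverse event rate, and the exposure is one injection of a tracer that the protocol describes as widely used.

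Most of this stands, and it keeps the point small. A reader might infer that 8.7 is the only safeguard that could halt the study; 9.1 shows that it is not. A reader might also infer that no subject will be asked about symptoms. The documents support only that asking is not required. Informal asking may occur, but it can vary between subjects and leaves no record of a negative answer.

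Two parts of the reply do not dispose of the point. The duties on serious events do not supply the frequency of non-serious effects. Observation by staff does not reach symptoms that are unvoiced and invisible.

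**Conclusion.** The point holds as a limited one. After the injection, capture is passive by the stated rule, no planned procedure adds to it, and the frequency that 8.7 weighs may be underestimated and lacks a denominator. The events affected are mainly unexpected, non-serious effects.

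Two stronger readings are tempting and are not supported. The first is that the frequency is in fact undercounted: the documents give neither a true rate nor a capture rate, so no undercount can be calculated, and with full capture there would be none. The second is that a stopping rule is miscalibrated: 8.7 is a judgement without a numeric boundary, so there is no rule whose operating characteristics could be wrong.

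The size is therefore illustrative. At a 10% true rate, the chance of recording nothing in 25 subjects goes from 7% with full capture to between 18% and 43% with two thirds or one third captured. These values rest wholly on the assumed rates, and the gap overstates what the proposed question would recover. Materiality is low. The change is worth making because it costs little.

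**What to change.** In section 9.2.1, add that every injected subject, including any later withdrawn or replaced, is asked one standard, non-leading question about symptoms since the injection before leaving the scan visit. The answer, including 'none', is entered in the eCRF. Report the count out of all injected subjects, and name it as the frequency meant in 8.7 and used in the annual safety report under 9.3. State that events after departure are still captured only passively.

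The cost is a short addition to 9.2.1, with a matching reference in 8.7 and 9.3, and one eCRF field. The question is put at a visit already planned, by staff already present. The downside is that more minor events will be recorded and must be followed under 9.4. No dose, schedule or clinical rule changes, and no threshold is added to 8.7.

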9.2.2 Serious adverse events (SAEs)

A serious adverse event is any untoward medical occurrence or effect that

- results in death;
- is life threatening (at the time of the event);
- requires hospitalisation or prolongation of existing inpatients' hospitalisation;
- results in persistent or significant disability or incapacity;
- is a congenital anomaly or birth defect; or
- any other important medical event that did not result in any of the outcomes listed above due to medical or surgical intervention but could have been based upon appropriate judgement by the investigator.

An elective hospital admission will not be considered as a serious adverse event.

The investigator will report all SAEs to the sponsor without undue delay after obtaining knowledge of the events.

The sponsor will report the SAEs through the web portal ToetsingOnline to the accredited METC that approved the protocol, within 7 days of first knowledge for SAEs that result in death or are life threatening followed by a period of maximum of 8

days to complete the initial preliminary report. All other SAEs will be reported within a period of maximum 15 days after the sponsor has first knowledge of the serious adverse events.

9.2.3 Suspected unexpected serious adverse reactions (SUSARs)

Adverse reactions are all untoward and unintended responses to an investigational product related to any dose administered.

Unexpected adverse reactions are SUSARs if the following three conditions are met:

1. the event must be serious (see chapter 9.2.2);
2. there must be a certain degree of probability that the event is a harmful and an undesirable reaction to the medicinal product under investigation, regardless of the administered dose;
3. the adverse reaction must be unexpected, that is to say, the nature and severity of the adverse reaction are not in agreement with the product information as recorded in the Investigator's Brochure.

The sponsor will report expedited the following SUSARs through the web portal ToetsingOnline to the METC:

- SUSARs that have arisen in the clinical trial that was assessed by the METC;
- SUSARs that have arisen in other clinical trials of the same sponsor and with the same medicinal product, and that could have consequences for the safety of the subjects involved in the clinical trial that was assessed by the METC.

The remaining SUSARs are recorded in an overview list (line-listing) that will be submitted once every half year to the METC. This line-listing provides an overview of all SUSARs from the study medicine, accompanied by a brief report highlighting the main points of concern.

The expedited reporting of SUSARs through the web portal Eudragilance or ToetsingOnline is sufficient as notification to the competent authority.

The sponsor will report expedited all SUSARs to the competent authorities in other Member States, according to the requirements of the Member States.

The expedited reporting will occur not later than 15 days after the sponsor has first knowledge of the adverse reactions. For fatal or life threatening cases the term will be maximal 7 days for a preliminary report with another 8 days for completion of the report.

9.3 Annual safety report

In addition to the expedited reporting of SUSARs, the sponsor will submit, once a year throughout the clinical trial, a safety report to the accredited METC, competent authority, and competent authorities of the concerned Member States.

This safety report consists of:

- a list of all suspected (unexpected or expected) serious adverse reactions, along with an aggregated summary table of all reported serious adverse reactions, ordered by organ system, per study;
- a report concerning the safety of the subjects, consisting of a complete safety analysis and an evaluation of the balance between the efficacy and the harmfulness of the medicine under investigation.

9.4 Follow-up of adverse events

All AEs will be followed until they have abated, or until a stable situation has been reached. Depending on the event, follow up may require additional tests or medical procedures as indicated, and/or referral to the general physician or a medical specialist. SAEs need to be reported till end of study within the Netherlands, as defined in the protocol

9.5 Data Safety Monitoring Board (DSMB)

A DSMB is deemed unnecessary because patients are exposed to a known diagnostic procedure with a low risk profile.

10. STATISTICAL ANALYSIS

10.1 Primary study parameter(s)

SUV will be calculated according to the following formula:

(measured activity concentration [MBq/mL] * body weight [g]) / injected activity [MBq]

The PET/CT images will be reconstructed in three dimensions. The PET and CT images will be fused and the SUVs will be aligned with CT to assess ⁶⁸Ga-PSMA uptake in tumor lesions, healthy salivary gland tissue, and the background.

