8. METHODS

8.1 Study parameters/endpoints

8.1.1 Main study parameter/endpoint

The SUV of ⁶⁸Ga-PSMA estimated with ⁶⁸GA-PSMA-PET scanning. If the SUV of tumor tissue is higher than the SUV of healthy salivary gland tissue and/or comparable to the SUV in prostate cancer, the level of PSMA expression is deemed high enough to pursue a therapeutic study with ¹⁷⁷Lu-PSMA.

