10.2 Secondary study parameter(s)

Tumor-to-background ratios and tumor-to-'healthy salivary gland tissue' ratios will be calculated using the SUV. It will be presented as mean and standard deviations.

Immunohistochemical PSMA expression on a tissue sample of the primary tumor will be quantified using a four point scale for tumor PSMA expression (0 = no expression, 1 = weak expression, 2 = moderate expression, and 3 = strong expression) and the number of PSMA-positive blood vessels per mm² will be counted.

The correlation between the immunohistochemical PSMA expression and tumor SUV will be evaluated using linear regression analysis. A p-value of <0.05 will be considered significant. Analyses will be performed using SPSS version 22.0.

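### Is the primary endpoint wrong because the SUV formula in section 10.1 does not mention decay correction?

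*Combined protocol and SAP*

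**What the plan says.** Section 10.1 gives the only definition of SUV: "measured activity concentration [MBq/mL] * body weight [g]) / injected activity [MBq". It states no time to which either activity refers. On image processing it adds "The PET/CT images will be reconstructed in three dimensions", followed by fusion with CT, and it says nothing about decay correction, applied or not. Section 8.3 sets the timing: patients are "injected with ⁶⁸Ga-PSMA with a dose of 2MBq/kg body weight" and the scan "will be performed 45-60 minutes post injection", covering "from groin to skull top, 3 minutes per bed position, 4-5 bed positions". Decay, half-life and a common reference time are mentioned nowhere.

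SUV is then used in three ways. Section 8.1.1 makes it the main endpoint and ties a therapeutic study to the condition "If the SUV of tumor tissue is higher than the SUV of healthy salivary gland tissue and/or comparable to the SUV in prostate cancer". Section 10.2 forms tumour-to-background and tumour-to-gland ratios. Section 10.2 also relates SUV to tissue staining: "The correlation between the immunohistochemical PSMA expression and tumor SUV will be evaluated using linear regression analysis".

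**The concern.** On a literal reading, the numerator is activity when the scanner records it and the denominator is activity when the dose is given. 68Ga decays appreciably over a wait of 45 to 60 minutes, so the quotient would be too low by an amount that depends on scan time. Correcting the image only to scan start would not help if the denominator stayed at injection time.

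Three uses would be exposed.

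- Absolute SUVs would be understated against decay-corrected prostate cancer values, which could make the second limb of the section 8.1.1 rule fail wrongly.
- Beds scanned later would lose more activity than beds scanned earlier. If acquisition ran from groin to skull, the salivary glands would be read last and tumour-to-gland ratios for lower lesions would be too high.
- Differences in start time would add spread to the regression of SUV on staining.

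Section 4.4 says the technique will be judged not valuable if it does not prove itself in these 25 patients, so a falsely low SUV would have consequences.

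**Working it through.** The plan states no SUV, decay factor or half-life, so it has no figure of its own to reproduce.

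**Inputs.** From section 8.3: scan at 45 to 60 minutes, and 4 to 5 beds of 3 minutes each. Assumed, not in the documents: 68Ga half-life T = 67.7 minutes, range 67.0 to 68.3.

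**Step 1: does the formula work?** Take a 70 kg patient given 2 MBq/kg, which is 140 MBq, spread evenly at 1 g/mL. The concentration referred to injection time is 140/70,000 MBq/mL, so SUV = (140/70,000) × 70,000/140 = 1.00, as it should be. Body weight cancels, so the result holds for any patient.

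**Step 2: what each reading gives at time t after injection.** The fraction of activity left is 2^(−t/T).

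- Concentration uncorrected, injected activity at injection: factor 2^(−t/T).
- Image corrected to scan start only, injected activity at injection: factor 2^(−t/T), with t the scan start.
- Image corrected to injection time, injected activity at injection: factor 1.00.
- Both referred to scan start: 2^(−t/T)/2^(−t/T) = 1.00.

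**Step 3: size under the first two readings.**

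- t = 45: 2^(−45/67.7) = 0.631 (0.628 to 0.633), 37% too low.
- t = 60: 2^(−60/67.7) = 0.541 (0.538 to 0.544), 46% too low.
- Starts at 45 and 60 minutes compared: 2^(15/67.7) = 1.166 (1.164 to 1.168), about 17%.

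**Step 4: ratios within a patient.** Tumour and gland share one injected activity, one body weight and one scan, so the common factor cancels. A remainder between beds arises only if beds are not individually corrected. First and last bed starts are 3 × 3 = 9 minutes apart with four beds and 4 × 3 = 12 minutes apart with five. The remainder is then at most 2^(9/67.7) = 1.10 to 2^(12/67.7) = 1.13, and close to 1.00 for structures in the same bed.

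**Step 5: the regression.** A factor common to all patients changes neither a correlation nor its p-value. Only the variable part matters. The decay rate is ln 2/67.7 = 0.01024 per minute. If starts were spread evenly over 15 minutes (an assumption), the added coefficient of variation is 0.01024 × 15/√12 = 0.044, or 4.4%. Suppose the between-patient SD of log SUV is 0.5 to 1.0 (an assumption) and start time is unrelated to uptake. A correlation on the log scale would then be multiplied by 1/√(1 + (0.044/0.5)²) = 0.996 at the lower value and 1/√(1 + (0.044/1.0)²) = 0.999 at the upper. That would not be noticed with 25 patients.

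**Step 6: the prostate cancer limb.** Section 8.1.1 gives neither a reference SUV nor a margin for comparability, so whether a given understatement would turn a pass into a fail cannot be computed. The limbs are joined by and/or, so failing this one does not by itself fail the rule.

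**The case for a change.** The strongest case for a change is that this is the only definition of the primary endpoint and that two of the four readings in step 2 give a value 37 to 46% too low. Even a statement that images are decay-corrected would not settle the matter, because the two activities need the same reference time. Absolute SUV feeds a go/no-go rule that refers to outside values, and the parameters listed in section 8.1.3 include neither injection time nor scan time. One sentence would remove the ambiguity at almost no cost.

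Much of this stands. The text is silent, the arithmetic is right for the assumed half-life, and a common time is required. What does not follow is that the faulty readings are the likely ones. The plan nowhere says that raw or scan-start activity will be divided by activity at injection. Comparing with prostate cancer SUVs makes sense only if SUV carries its ordinary meaning, with both activities on one time base. The tracer is made in the hospital's own radiology and nuclear medicine department (section 6.8), and section 11.4 describes the scan as part of normal care in prostate cancer. Section 8.3 sets scanning relative to injection, so both times must be known for the procedure to be followed. A written sentence would record the convention without altering what competent analysts do.

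**Conclusion.** The omission is real, but an error in the endpoint is not shown. Section 10.1 gives a generic SUV formula that is exact once both activities share a reference time, and that is a routine processing step.

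The understatement of 37% at 45 minutes and 46% at 60 minutes rests on two assumptions: a 68Ga half-life near 67.7 minutes, and no correction to a common time anywhere in the processing. The documents support neither assumption, and the second departs from ordinary practice. Even then, tumour-to-gland comparisons would be largely unaffected (at most 10 to 13% between the end beds, and only without bed-by-bed correction), and the regression would hardly move. Absolute SUV and the prostate cancer comparison would be exposed, with an effect on the decision that cannot be calculated. This is a gap in detail that analysts fill sensibly, and no change to the plan follows. The conclusion would differ if the processing records showed that the two activities had been taken at different times.
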